Increasing Documentation and Disclosure of Sickle Cell Trait Status: An Implementation Science Approach

NCT05387564

Document Date: September 1, 2023
Updated cover page: October 21, 2025

Increasing Documentation and Disclosure of Sickle Cell Trait Status: An Implementation Science Approach: SCTalk

COMPLIANCE STATEMENT

This study will be conducted in full accordance with all applicable Nemours Research Policies and Procedures and all applicable Federal and state laws and regulations including 45 CFR 46. All episodes of noncompliance will be documented.

The investigators will perform the study in accordance with this protocol, will obtain consent, and will report unanticipated problems involving risks to subjects or others in accordance with Nemours IRB Policies and Procedures and all federal requirements. Collection, recording, and reporting of data will be accurate and will ensure the privacy, health, and welfare of research subjects during and after the study.

STUDY OBJECTIVES

A two-arm, randomized, interrupted time series design will compare an “all-in” and “add-in” approach to a suite of intervention strategies to increase PCP’s EHR documentation and disclosure of NBS results and SCT status during infancy. This is a pilot study. The main goal of this pilot study is to establish a reliable estimate of the effect size of a suite of intervention strategies.

Primary Objectives (Aim)

Using an implementation framework we will assess and compare the acceptability, feasibility, self-efficacy, and time costs of using the intervention strategies when delivered “all-in” versus “add-in” by measuring the following outcomes.

- Acceptability: via PCP survey for each toolkit component.
- Feasibility: Percent of PCPs who use individual toolkit components.
- Adoption/Self-efficacy: PCP survey. Intention and confidence to document/discuss NBS/SCT result.
- Cost: PCP survey: Perceived time (in mins) to document and discuss NBS/SCT result, effect on other discussion topics during the visits.
- Penetration (via interrupted time series): via EHR extraction. Rate of scanned NBS results available in the EHR. Rate of documentation and disclosure of NBS and SCT result at < 2 months of age in each of the following: the problem list, the medical history section, and progress note. Evaluate monthly: retrospectively (pre intervention) and prospectively (post intervention).

Secondary Objective (Aim)

[figure not shown]

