- Feasibility: Percent of PCPs who use individual toolkit components.
- Adoption/Self-efficacy: PCP survey. Intention and confidence to document/discuss NBS/SCT result.
- Cost: PCP survey: Perceived time (in mins) to document and discuss NBS/SCT result, effect on other discussion topics during the visits.
- Dispersion: Via EHR extraction- Proportion of children over 2 months of age who have NBS/SCT newly documented (as above).
- Knowledge: Caregiver survey- Proportion of caregivers who accurately reported their child's NBS result.
- Inequities in documentation: Via chart review. Demographic data for each infant: primary care site, sex, race, ethnicity, and insurance type.
- Satisfaction: Caregiver survey.

Statistical Methods

Unit of analysis will be the individual PCP (i.e. pre/post) and by trial arm with the primary end point being the rate of documentation and disclosure of NBS and SCT (penetration).

Data will be summarized in numeric and graphic forms. Mean and standard deviation or median and interquartile range will be used for summarizing numerical variables and frequencies and percentages will be used for categorical variables. PCP's EHR documentation and disclosure of newborn screen (NBS) and sickle cell trait (SCT) carrier results will be presented by pre-post intervention as well as by intervention groups. The primary end point of the study is to compare the proportion of PCP's/ EHR documentation and disclosure of NBS and SCT between pre- and post- intervention periods.

Generalized linear mixed effects model will be used for the analysis of the primary end-point. Odds ratio with confidence interval will be provided for the documentation and disclosure. Generalized linear mixed effects model will also be used to compare the proportion of post-intervention documentation and disclosure over time (monthly) between two intervention groups. Mean score of acceptability for each intervention (A, B, C) as well as mean total score for all three interventions will be compared between two intervention groups. Similarly, other survey results such as Self-Efficacy of PCP to document NBS and time cost will be compared between two intervention groups. Also, dispersion, caregiver knowledge and caregiver satisfaction will be

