compared between two groups. Two sample t-test, Mann-Whitney U-test, Chi-square test, analysis of variance (ANCOVA), liner mixed effects model, logistic regression, and mixed effects logistic regression will be used, for the above comparisons, as appropriate. PCP nested within clinic will be used as the random effects in the model as needed. All tests will be two-tailed with an overall level of significance of 0.05. Benjamini-Hochberg method will be used to adjust the level of significance for multiple comparisons. Statistical software packages SPSS, SAS (version 9.4) or latest version of R will be used for the analysis.

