Sample Size Justification: This is a pilot study and there is no reported effect size on the intervention of this study in the literature. Therefore, the main goal of this study is to explore reliable effect size that would assist designing future studies with formal hypothesis testing. The primary aim of the study is to increase PCP's EHR documentation and disclosure of NBS and SCT carrier results during infancy (age less than 1 month). It has been found in a chart review that 71% of newborns over the last 3 years had a newborn screen result scanned into their chart. The goal of this study is to raise this to 90%. A sample size of 74 in each of the pre- and post-intervention period can detect the targeted difference in newborn screen of 19% with 86% power at the level of significance of 0.05. PCP documentation has been reported as 20% in the literature. We aim to raise this 50%. Again, a sample size of 43 in each of the pre- and post-intervention period would be adequate to detect the targeted difference in the PCP documentation with a power of 85% at the level of significance of 0.05. Currently 53% sickle cell traits has been documented. Once again, the goal is to raise this to 90%. A sample size of 21 infants with sickle cell traits (SCT) in each of pre- and post-intervention periods would be adequate to detect this difference in this documentation with a power of 80% at the level of significance of 0.05. In DE, the prevalence of SCT is 2.1% in overall children and about 7% in African Americans. Considering 2.1% SCT in overall children, we need 1000 infants to screen in each of the pre-and post-intervention periods, to detect the targeted difference with a power of 80% at the level of significance of 0.05. The study plans to recruit 10 PCPs in each of the intervention arm (20 PCP in both arms). About 6-10 infants are expected to be seen by a PCP in a month and 54-90 new infants are expected to be seen by a physician during 9 months of post intervention period. We expect that minimum of $540 \times 2 = 1080$ patients (540 for each intervention) to be seen by 20 PCPs. Therefore, a minimum sample size of 1080 infants is planned for each of the pre-and post-intervention periods for this study. The planned minimum sample size of 1080 in the post intervention period would also be adequate to determine the effect size for survey results and documentation and disclosures for each intervention arm separately.

Analysis of Qualitative Data:

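### On its ordinary reading, the random-effects statement leaves between-PCP and between-clinic variation in the toolkit effect out of the primary pre/post interval

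*Combined protocol and SAP*

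**What the plan says.** In the combined protocol and SAP, Statistical Methods defines the primary comparison as "documentation and disclosure of NBS and SCT between pre- and post- intervention periods". On the model it says "Generalized linear mixed effects model will be used for the analysis of the primary end-point", and on the estimate "Odds ratio with confidence interval will be provided for the documentation and disclosure".

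The random effects get one sentence: "PCP nested within clinic will be used as the random effects in the model as needed". It comes after the list of methods for the survey and other secondary comparisons. The section names no PCP-by-period or clinic-by-period term, robust variance, cluster-level analysis or small-sample correction. It does say "Unit of analysis will be the individual PCP (i.e. pre/post) and by trial arm", without stating how that enters the mixed model. On testing: "All tests will be two-tailed with an overall level of significance of 0.05".

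Study Objectives gives the purpose of the pilot as to "establish a reliable estimate of the effect size of a suite of intervention strategies".

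**The concern.** A random intercept for PCP or clinic absorbs a tendency to document more or less in both periods. That tendency largely cancels from a pre/post contrast. What remains, beyond binomial noise, is how much the *change* differs from PCP to PCP and clinic to clinic. An intercept-only model treats the change as common to all, so each infant counts as independent information about it.

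The plan itself gives reason to expect the change to differ. Feasibility is defined by the share of PCPs who take up each component, so uptake is expected to be partial. The toolkit descriptions and the roll-out section let each site choose how the material is delivered.

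At stake is the pilot's main product. An interval that overstates precision, with no estimate of how far the effect varies, is a weak basis for sizing the multi-site trial that is meant to follow. The nominal 0.05 level of the primary test would also be exceeded.

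**Working it through.** **Inputs from the documents.** Sample Size Justification: 20 PCPs; 6 infants per PCP per month at the low end over 9 months, so 6 × 9 = 54 per PCP and 54 × 20 = 1080 per period. Planned changes: 71% to 90% for scanned newborn screen (NBS) results (baseline: "71% of newborns over the last 3 years had a newborn screen result scanned into their chart"), 20% to 50% for PCP documentation, 53% to 90% for SCT documentation. SCT prevalence is 2.1%. The site section requires at least 2 sites per arm, so 4 clinics.

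**The plan's own figures.** Power for two independent proportions by the arcsine formula, two-sided 0.05, is Φ(|h|√(n/2) − 1.96) with h = 2 asin√p2 − 2 asin√p1:
- 74 per period, 71% to 90%: h = 0.494, power 85.2% (stated 86%)
- 43 per period, 20% to 50%: h = 0.644, power 84.7% (stated 85%)
- 21 per period, 53% to 90%: h = 0.867, power 80.2% (stated 80%)

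These reproduce to within 1 point with no clustering term, so the sample size treats infants as independent.

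**Standard error of the pre/post log-odds ratio.** With slope SDs τP (PCP) and τC (clinic):

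Var = 1/(N p1 q1) + 1/(N p2 q2) + τP²/20 + τC²/4

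An intercept-only model reports approximately the first two terms. With N = 1080:
- 71% to 90%: 0.00450 + 0.01029 = 0.01479, SE 0.122
- 20% to 50%: 0.00579 + 0.00370 = 0.00949, SE 0.097

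The omitted terms are 0.3²/20 = 0.0045 or 0.5²/20 = 0.0125 for PCPs, and 0.3²/4 = 0.0225 for clinics. **The slope SDs are assumptions; the documents give none.** Approximate coverage of the nominal 95% interval is 2Φ(1.96/ratio) − 1.

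| τP | τC | SE ratio, 71→90 | SE ratio, 20→50 | Coverage by formula, 71→90 / 20→50 | Simulated coverage, 71→90 / 20→50 |
|---|---|---|---|---|---|
| 0 | 0 | 1.00 | 1.00 | 95% / 95% | 95.1% / 95.2% |
| 0.3 | 0 | 1.14 | 1.21 | 91% / 89% | 90.3% / 89.0% |
| 0.5 | 0 | 1.36 | 1.52 | 85% / 80% | 80.2% / 79.8% |
| 0.3 | 0.3 | 1.68 | 1.96 | 76% / 68% | 74.5% / 70.0% |
| 0.5 | 0.3 | 1.84 | 2.17 | 71% / 63% | 66.9% / 64.0% |

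The simulation used 2000 trials per row, 4 clinics × 5 PCPs × 54 infants per period, normal slopes, and intercept SDs of 0.5 (PCP) and 0.3 (clinic). The fitted model had one intercept per PCP and a common period effect, as a stand-in for the random-intercept model. In the same setting with a mean effect of zero, the two-sided 0.05 test rejected in about 5% of trials with no slope variation, 10% to 11% at τP = 0.3, 23% at τP = 0.5, and 28% to 33% with both SDs at 0.3.

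**On the odds-ratio scale, 20% to 50% (OR 4.00).** The intercept-only 95% interval is 3.30 to 4.84. With both SDs at 0.3 the SE is √(0.00949 + 0.0045 + 0.0225) = 0.191, giving 2.75 to 5.82 with the normal quantile, or 2.18 to 7.35 with t on 3 df (3.182).

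**SCT documentation, 53% to 90%.** 2.1% of 1080 is about 23 infants per period, roughly one per PCP. Binomial variance is 0.177 + 0.490 = 0.667, SE 0.82. With τP = 0.5 and τC = 0.3 the SE is √(0.667 + 0.035) = 0.84, ratio 1.03. With both at 0.5 it is √(0.667 + 0.075) = 0.86, ratio about 1.05.

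**The case against.** **The plan does not exclude a period slope.** It is silent on intercept versus slope. A reader might infer that the plan commits to an intercept-only model; it does not. The clause about need makes even the PCP and clinic effects conditional, and the sentence's position leaves its link to the primary model unclear. This stands and sets the wording of the point. It does not remove the point: the text permits the intercept-only model, and that is what the phrase ordinarily means.

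**The unit of analysis is said to be the PCP, pre/post.** If each PCP's change were the unit, between-PCP variation in change would enter the interval. But the plan does not connect this to the mixed model, and the sample size counts infants. It leaves the matter open.

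**The size rests on assumed SDs.** This stands. A reader might infer that the interval claims about twice its real precision. That needs an assumed clinic slope SD of about 0.3 as well as PCP variation; PCP variation alone gives 1.1 to 1.5 fold, and zero variation gives none.

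**Not every component is affected.** This also stands. The SCT component, which drives the requirement for 1000 infants per period, is dominated by binomial noise, and a PCP slope can hardly be estimated there.

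**Four clinics cannot support a clinic slope variance.** This stands too. Fitting clinic-by-period as fixed and averaging is not a full remedy, because it drops the clinic term from the interval. For 20% to 50% with τP = 0.5 and τC = 0.3, the SE would be 0.148 against 0.211, with coverage of about 83% for a wider population of clinics.

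**Conclusion.** The concern holds in a conditional form. On the ordinary reading of the random-effects sentence, the primary pre/post interval omits variation in the toolkit effect between PCPs and clinics, and it is too narrow whenever that variation is not zero. The documents make some variation likely but give no figure for it. For the high-volume outcomes, the understatement of the SE is 1.1 to 1.5 fold for PCP slope SDs of 0.3 to 0.5, and about 1.7 to 2.2 fold with a clinic slope SD of 0.3 added. For SCT documentation it is negligible.

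These figures assume equal cluster sizes, normal slopes, exactly 4 clinics, and 1080 infants in both periods. More clinics would shrink the clinic term. Fewer infants would shrink the ratios: with 600 per period (6 per month × 5 months × 20 PCPs, if the roughly 5-month site participation applied), the 20% to 50% binomial variance is 0.00949 × 1080/600 = 0.0171. The ratio with both SDs at 0.3 is then √(1 + 0.027/0.0171) = 1.6 instead of 1.96. The direction does not change.

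**What to change.** In Statistical Methods, for the high-volume components (scanned NBS, NBS documentation and disclosure):

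- State that the primary mixed model includes a PCP-by-period random effect, with small-sample degrees of freedom. When only PCPs vary, this restores coverage to about 95%.
- Report the estimated PCP-by-period variance, for use in planning the next trial.
- Report clinic-specific odds ratios.
- Add a clinic-level sensitivity analysis: the mean of the clinic log-odds ratios, with a t interval on clinics minus 1 degrees of freedom (3 with 4 clinics). This carries clinic variation without having to model its variance.
- If clinic-by-period is fitted as a fixed effect, state that the interval applies to these clinics only.

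For SCT documentation, no PCP slope is needed.

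The cost is SAP wording; no new data are required. The downside is a wider interval, and a much wider one at clinic level: in the example with both SDs at 0.3, 2.18 to 7.35 around an odds ratio of 4.00.

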Practice level data from the medical record. For each practice location: Patient level demographics (based on having been seen for a well child exam in the 3 years prior to data extraction) will be linked with the primary practice location at the start of the trial. Practice level data will be obtained from a retrospective evaluation of available EHR data and focus on.

- Age and gender distribution
- Race and Ethnicity distribution
- Insurance make-up (Private, Medicaid, other)
- Zipcode to assess median household income of patients seen at that location (census data), Childhood Opportunity Index (COI)
- Number and portion of the patient population with SCT documented in the problem list, medical history section, and diagnosis codes

PCP Consent and Demographic Survey:

Toolkit components will be available to PCPs and office staff in all trial sites regardless of their participation in the research portion of the trial. Use of the toolkit components is as an educational aid and to facilitate routine patient care.

PCPs will initially be approached for consent for the research portion of the trial prior to toolkit initiation. For PCPs who elects to participate in the longitudinal research portion of the trial, a general demographic survey will be completed at time of initial consent. The demographic survey will be facilitated by REDCap and administered electronically. PCPs may enroll at any time during the trial though first attempt at consent will be before toolkit initiation at with each toolkit component rollout and survey point.

“Roll-out” of toolkit components:

- “All-in” arm: The “all-in” trial arm will have access to and be educated regarding the intervention components at one time point via email, via discussion at lunch & learn, via office meeting, or via virtual meeting or recording (depending on site preference).
- “Add-in” arm: Each PCP in the “add-in” arm will receive the intervention components in the same sequence (within a 1 month timeframe of other offices in the “add-in” arm) with 1 component added every 6 weeks.

With each toolkit component rollout an email will be sent to the office staff reminding them about the project, alerting them to the new component, and notifying them about a virtual Teams “office hours” where the study PI will be available for questions or concerns. The study PI will also be available for any virtual or in-person education an office site may request (ie at an office meeting, etc)

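### 1080 infants do not support per-arm SCT effect sizes (about 11 SCT infants per arm) or, by themselves, survey precision; the 80% SCT power depends on identifying every SCT infant

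*Combined protocol and SAP*

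**What the plan says.** All the figures are in the Sample Size Justification of the combined protocol and SAP. It sizes three documentation targets, each as a pre/post comparison at the 0.05 level:

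- Scanned NBS result: 71% to 90%, 74 infants per period, 86% power. The baseline is that "71% of newborns over the last 3 years had a newborn screen result scanned into their chart".
- General PCP documentation: 20% to 50%, 43 per period, 85% power.
- SCT documentation: 53% to 90%, 21 SCT infants per period, 80% power. The baseline is "Currently 53% sickle cell traits has been documented".

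Prevalence converts the 21 into a screening number: "In DE, the prevalence of SCT is 2.1% in overall children and about 7% in African Americans", and then "Considering 2.1% SCT in overall children, we need 1000 infants to screen in each of the pre-and post-intervention periods".

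The supply side is 10 PCPs per arm and a 9-month post-intervention period: "About 6-10 infants are expected to be seen by a PCP in a month". At 6 a month this gives 540 per arm, so "a minimum sample size of 1080 infants is planned for each of the pre-and post-intervention periods". The section closes by saying that 1080 in the post-intervention period "would also be adequate to determine the effect size for survey results and documentation and disclosures for each intervention arm separately". No calculation accompanies that sentence.

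SCT status is to come from EHR extraction and manual chart review (Study Procedures, on documentation and discussion of results). Under Caregiver Survey Recruitment, the NBS result is reviewed only where the EHR has it. The practice-level data include "SCT documented in the problem list, medical history section, and diagnosis codes". The planned survey samples, under Total Number of Study Sites/Total Number of Subjects Projected, are at least 10 PCPs per arm and 500 caregivers.

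**The concern.** SCT documentation is part of the primary endpoint, and it alone drives the need for about 1000 infants per period; the other two targets need 74 and 43. The pilot's declared goal is a reliable effect size for a later trial. Two statements about this component go further than the figures behind them.

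First, the per-arm adequacy sentence makes no distinction between outcomes measured on every infant and an outcome measured on about 2 in 100. It also applies an infant count to surveys answered by PCPs and caregivers. A later trial sized on per-arm SCT estimates from about 11 infants could be badly mis-sized.

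Second, the conversion from 21 to 1000 uses prevalence alone. The same paragraph reports that 29% of charts have no scanned result, and the plan does not say how SCT status is established in those charts. The problem list, history and diagnosis codes can reveal status, but they are themselves the documentation being measured. An SCT infant with neither a scan nor an entry would drop out of the denominator.

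**Working it through.** All calculations ignore clustering by PCP and clinic.

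**Reproducing the plan.** The arcsine formula for two proportions fits the plan's SCT figure best: h = 2·asin(√p2) − 2·asin(√p1), power = Φ(h·√(n1·n2/(n1+n2)) − 1.96).

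- 53% vs 90%: h = 0.867; 21 and 21 give 80.2% (stated 80%).
- 71% vs 90%: 74 and 74 give 85.2% (stated 86%).
- 20% vs 50%: 43 and 43 give 84.7% (stated 85%).
- Screening number: 21/0.021 = 1000, exact.
- Supply: 20 PCPs × 6 × 9 = 1080; 10 × 6 × 9 = 540 per arm.

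**SCT infants per arm, assuming every one is identifiable.**

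| Infants per PCP-month | Infants per arm | SCT infants at 2.1% | Half-width of pre/post difference |
|---|---|---|---|
| 6 | 540 | 11.3 | 34 points |
| 10 | 900 | 18.9 | 26 points |

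The half-width is 1.96·√((0.53·0.47 + 0.90·0.10)/n), with the pre-period assumed to split equally between arms as the post-period does. For n = 11.34 it is 0.339, against a target change of 90 − 53 = 37 points. Using the post-period alone, 10 of 11 documented has a 95% Wilson interval of 62% to 98%.

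For the other two outcomes, 540 per arm is well above 74 and 43, so on the plan's own unclustered terms the sentence holds for them.

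**Surveys.**

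- PCP arm difference with 10 per arm: t(0.975, 18)·√(2/10) = 2.10 × 0.447 = 0.94 SD.
- Caregiver proportion, if all 500 are post-intervention and split 250/250 (assumed), at 50%: 1.96·√(2·0.25/250) = about 9 points.

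Neither formula contains 1080.

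**Pooled SCT power at 1080 per period.** Expected SCT infants are 1080 × 0.021 = 22.7 per period. The 53% and 90% are taken as the rates among the infants counted.

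| Who can be counted | Pre | Post | Power |
|---|---|---|---|
| Every SCT infant | 22.7 | 22.7 | 83% |
| Only scanned results, 71% then 90% | 16.1 | 20.4 | 74% |
| Only scanned results, 71% throughout | 16.1 | 16.1 | 69% |

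These are not bounds. Suppose infants are identified by a scan or an entry, independently. Then 22.7 × (1 − 0.29·0.47) = 19.6 and 22.7 × (1 − 0.10·0.10) = 22.5 are counted, and power is about 80%. If 53% and 90% are instead rates among all SCT infants, the rates among those counted become 61% and 91%, and power is about 65%.

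Other inputs push upward. With scanned results only (71% then 90%), 7 infants per PCP-month (1260 per period) gives 80%, 8 gives 85% and 10 gives 92%. At 1080, prevalence of 2.44% also restores 80%.

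**The basis of 1080.** It uses 9 months. Duration of Study Participation gives about 5 months per site, and the caregiver survey section describes a 6-month retrospective period. At 6 per PCP-month, 20 PCPs see 20 × 6 × 6 = 720 infants before and 20 × 6 × 5 = 600 after. That is 15.1 and 12.6 SCT infants, and about 62% power with every one identified.

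**The case against.** The best defence of the per-arm sentence is that this is a pilot, that the sentence speaks of determining an effect size and not of power, and that it does not name SCT. That is fair as far as it goes, and a per-arm power figure would test a claim the plan does not make. But the stated goal is a reliable estimate, SCT documentation falls within the documentation the sentence covers, and an interval nearly as wide as the target effect is not reliable. The half-width does need an assumed pre-period split; the count of about 11 and the post-only interval do not.

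A reader might infer that the whole per-arm sentence fails. It does not: scanning and general documentation are well estimated at 540 per arm before clustering. Nor are infant numbers irrelevant to the caregiver survey, because caregivers are drawn from the identified infants. The point is that precision follows the number who respond.

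On power, a reader might infer that 1000 is a miscalculation, or that the trial is underpowered for SCT. The documents support neither. The division is right. The 71% is the share of results scanned, not the share of SCT infants who can be identified, since an unscanned infant may be recognised from the problem list, history or notes. In addition, 1080 is called a minimum, and offices are purposively chosen for a wide racial mix, which may raise prevalence above 2.1%. It would be equally wrong to read 74% to 83% as a range, because reasonable cases fall outside it on both sides.

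**Conclusion.** The per-arm adequacy statement is unsupported for SCT documentation. About 11 SCT infants per arm are expected at the planned minimum, and about 19 at the plan's highest throughput, against its own requirement of 21 per period. This needs no assumption about scanning, only the stated 2.1% prevalence; higher prevalence at the chosen offices would ease it. For surveys the statement cites the wrong unit, and with 10 PCPs per arm an arm difference is known only to within about 0.94 SD.

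The 80% power for SCT is conditional, not shown to be wrong. It holds at 1000 only if every SCT infant can be identified, which the plan neither states nor arranges for. The illustrative values at 1080 (83%, 74%, 69%) depend on how status is ascertained and on scanning rates, and higher throughput or prevalence would offset the loss. All of them take 1080 as given, and its 9-month basis does not match the periods stated elsewhere. None allows for clustering, which would normally reduce precision further.

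**What to change.** 1. Limit the per-arm adequacy sentence to NBS scanning and general PCP documentation, noting that clustering is ignored. Label per-arm SCT results descriptive, with about 11 SCT infants expected per arm at the minimum.
2. Base survey adequacy on the number of PCPs and of responding caregivers.
3. Write the SCT yield as N × prevalence × proportion identifiable. Say how SCT status is established when no result is scanned, and present the 80% power as conditional on that. If the power values above are shown, call them illustrations, not limits.
4. Before restating any power, reconcile the 9 months behind 1080 with the roughly 5 months of site participation and the 6-month retrospective period.

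The cost is text edits and one ascertainment rule. No design change follows from items 1 to 3. The price is a less favourable stated basis for SCT. Item 4 may lower the planned number of infants if the shorter periods are the ones in force.
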